5.4.5.2. HBsAg Thresholds

The following cut-offs for HBsAg values and decreases from baseline will be used in separate summaries over time by intervention arm. The number and proportion of participants who meet those HBsAg thresholds during the study will be summarized descriptively by intervention arm and analysis phase over time.

Thresholds for **HBsAg values**:

- <1000 IU/mL
- <100 IU/mL
- <10 IU/mL
- <1 IU/mL
- <0.05 IU/mL

Thresholds for **HBsAg decreases from baseline**:

- $\geq 0.3 \log_{10}$ IU/mL
- $\geq 0.5 \log_{10}$ IU/mL
- $\geq 1 \log_{10}$ IU/mL
- $\geq 2 \log_{10}$ IU/mL
- $\geq 3 \log_{10}$ IU/mL
- $\geq 4 \log_{10}$ IU/mL

Cumulative percentage of participants achieving any given decrease from baseline in HBsAg at Week 72 and at Week 96, separately, will be presented graphically.

5.4.5.3. HBeAg Thresholds

The following cut-offs for HBeAg values and decreases from baseline will be used in separate summaries over time by intervention arm for the subset of participants with HBeAg positive at baseline. The number and proportion of participants who meet those HBeAg thresholds during the study will be summarized descriptively by intervention arm and analysis phase over time.

Thresholds for **HBeAg** values:

- < 100 IU/mL
- < 10 IU/mL
- < 1 IU/mL
- < LLOQ (0.11 IU/mL)

Of note, seroclearance of HBeAg is defined as (quantitative) HBeAg<LLOQ.

Thresholds for **HBeAg** decreases from baseline:

- $\geq 0.3 \log_{10}$ IU/mL
- $\geq 0.5 \log_{10}$ IU/mL
- $\geq 1 \log_{10}$ IU/mL
- $\geq 2 \log_{10}$ IU/mL
- $\geq 3 \log_{10}$ IU/mL

Cumulative percentage of participants achieving any given decrease from baseline in HBeAg at Week 72 and at Week 96, separately, will be presented graphically.

5.4.5.4. HBV DNA Thresholds

The values and decreases from baseline of HBV DNA will be summarized by treatment history (not currently treated and virologically suppressed).

The following cut-offs for HBV DNA values and decreases from baseline will be used in separate summaries over time by intervention arm. The number and proportion of participants who meet those HBV DNA thresholds during the study will be summarized descriptively by intervention arm and analysis phase over time.

Thresholds for **HBV DNA** values:

- < LLOQ for target detected and not detected
- < LLOQ for target not detected
- < LLOQ for target detected
- <60 IU/mL
- <100 IU/mL
- <200 IU/mL

- <1000 IU/mL
- <2000 IU/mL
- <20000 IU/mL

Thresholds for **HBV DNA** decreases from baseline:

- $\geq 1 \log_{10}$ IU/mL
- $\geq 2 \log_{10}$ IU/mL
- $\geq 3 \log_{10}$ IU/mL
- $\geq 4 \log_{10}$ IU/mL
- $\geq 5 \log_{10}$ IU/mL

Cumulative percentage of participants achieving any given decrease from baseline in HBV DNA at Week 72 and at Week 96, separately, will be presented graphically.

5.4.6. Thresholds Based on Multiple Markers

The number and proportion of participants who meet the following blood marker reduction/seroclearance thresholds at 12, 24, 36 and 48 weeks, respectively, after stopping all study interventions (including NA) and not having NA re-treated will be summarized descriptively by intervention arm for each marker and each threshold listed below.

- **HBsAg<LLOQ and HBV DNA**
 - HBsAg<LLOQ and HBV DNA<LLOQ^{**}
 - HBsAg<LLOQ and HBV DNA \geq LLOQ
- **HBsAg \geq LLOQ and HBV DNA<2,000 IU/ml**
 - HBsAg \geq LLOQ and HBV DNA<LLOQ^{**}
 - HBsAg \geq LLOQ and LLOQ \leq HBV DNA<2,000 IU/ml (See partial cure in Section 5.4.7)
- **HBsAg \geq LLOQ and HBV DNA \geq 2,000 IU/ml**
 - HBsAg<100 IU/mL and HBV DNA \geq 2,000 IU/ml
 - HBsAg \geq 100 IU/mL and HBV DNA \geq 2,000 IU/ml

^{**} HBV DNA<LLOQ will be summarized by DNA target detected, TND and overall.

Due to the exploratory objectives of this Phase 2b study, additional blood marker reduction/seroclearance thresholds may be added at a later point in time according to the clinical interest.

5.4.7. Partial Cure

Partial cure will be evaluated at each of the following time points separately: 24 weeks and 48 weeks after stopping all study interventions. A participant will be defined as having achieved partial cure if he/she has:

- Stopped all study interventions at any time, and
- had HBV DNA level < 2,000 IU/ml quantifiable at the given week of interest, and
- had HBsAg \geq LLOQ at the given week of interest, and
- not required NA re-treatment after stopping all study interventions.

The number and proportion of participants who achieve partial cure during the study will be summarized descriptively by intervention arm at 24 weeks and 48 weeks after stopping all study interventions, respectively. Of note, HBV DNA level < 2,000 IU/ml may be achieved prior to the Week 24 (or 48) but must be observed at the given week of interest. Proportions will be analyzed using the Mantel-Haenszel test and 90% CIs stratified for treatment history status and screening HBeAg status.

If the HBV DNA value 24 weeks after stopping all study interventions is missing, the LOCF in conjunction with the next available observation imputation approach will be used. The available non-missing lab test closest to 24 weeks after stopping all study interventions which is no earlier/later than 12 weeks from the actual time point of interest (12 and 36 weeks after stopping all study interventions, respectively) will be imputed.

If the HBV DNA value at 48 weeks after stopping all study interventions is missing, the LOCF imputation approach will be used. The last available lab test no earlier than 36 weeks after stopping all study interventions will be carried forward.

5.4.8. Treatment Failure

Treatment failures will be summarized separately on-treatment, off-treatment, and overall.

A participant will be defined as on-treatment failure if he/she never met the criteria for stopping NA treatment during the study. The number and proportion of on-treatment failure participants will be summarized descriptively by intervention arm over time (i.e. at Week 48, Week 60, Week 72 and Week 96, respectively) and at the time of EOT.

A participant will be defined as off-treatment failure if he/she required NA re-treatment after stopping all study interventions. The number and proportion of off-treatment failure participants will be summarized descriptively by intervention arm over time (i.e. at 12, 24 and 48 weeks after stopping all study interventions, respectively).

5.4.9. HBsAg Seroconversion

Seroconversion of HBsAg is defined as having achieved HBsAg seroclearance together with appearance of anti-HBs antibodies.

Seroclearance of HBsAg is defined as (quantitative) HBsAg < LLOQ. Appearance of anti-HBs antibodies is defined as a baseline anti-HBs antibodies (quantitative) < LLOQ and a post-baseline assessment \geq LLOQ. A sensitivity analysis will be conducted using the threshold of 10mIU/mL, i.e. appearance of anti-HBs antibodies is defined as a baseline anti-HBs antibodies (quantitative) < 10 mIU/mL and a post-baseline assessment \geq 10 mIU/mL.

The seroconversion will only be assessed at the time points when the anti-HBs antibodies assessment is available. If the HBsAg value is missing at that specific time point, then the non-missing lab test closest to that specific timepoint will be used. If the non-missing lab test before and after the specific timepoint fall equidistant from the target timepoint, the later one will be used to impute the missing value.

The number and proportion of participants who achieve HBsAg seroconversion will be summarized descriptively by intervention arm and analysis phase.

For participants achieving HBsAg seroconversion, descriptive statistics will be calculated for the level of anti-HBs antibodies at the timepoint when achieving the HBsAg seroconversion by intervention arm. In an additional summary, the level of anti-HBs antibodies at the specific timepoint (i.e. Week 48, Week 72, Week 96) will be summarized for the subset of the participants achieving HBsAg seroconversion at any time before or at that given timepoint by intervention arm.

In addition, the number and proportion of participants with appearance of anti-HBs antibodies but without seroclearance of HBsAg will also be summarized by intervention arm and analysis phase.

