To evaluate the safety and tolerability of the study intervention throughout the study.	• Proportion of participants with (serious) adverse events ([S]AEs) and abnormalities in clinical laboratory tests (including hematology, blood biochemistry, blood coagulation, urinalysis, urine chemistry, and renal biomarkers), 12-lead electrocardiograms (ECGs), and vital signs.							

Objectives	Endpoints
• To evaluate the efficacy of the study intervention during the follow-up phase*.	Proportion of participants with HBsAg seroclearance 24 weeks after completion of all study intervention at Week 48.
	Proportion of participants with HBsAg seroclearance 48 weeks after completion of all study intervention at Week 48.
	• Proportion of participants with HBV DNA <lower (lloq)="" 24="" 48="" 48.<="" after="" all="" and="" at="" completion="" intervention="" limit="" of="" quantification="" respectively,="" study="" td="" week="" weeks,=""></lower>
	Proportion of participants meeting the NA treatment completion criteria during follow-up.
	Proportion of participants with HBsAg seroclearance 24 and 48 weeks, respectively, after completion of NA treatment at any time during follow-up.
	Frequency of flares.
	Proportion of participants requiring NA re-treatment during follow-up (see NA Re-treatment Criteria and Monitoring After Stopping of NA).
• To evaluate efficacy as measured by blood markers (such as HBsAg, HBeAg,** HBV DNA, and alanine aminotransferase [ALT]) during study intervention and follow-up.	Proportion of participants with (sustained) reduction, suppression, and/or seroclearance considering single and multiple markers (such as HBsAg, HBeAg,** HBV DNA and ALT).
	Proportion of participants with HBsAg and HBeAg** seroconversion.
	Change from baseline over time in HBsAg, HBeAg,** and HBV DNA.
	• Time to achieve HBsAg and HBeAg** seroclearance.
	• Proportion of participants with HBsAg levels and/or changes from baseline below/above different cut-offs (eg, HBsAg <100 IU/mL or >1 log ₁₀ IU/mL reduction in HBsAg from baseline).
	Proportion of HBeAg-positive participants with HBeAg** levels and/or changes from baseline below/above different cut-offs.
	Proportion of participants with HBV DNA levels and/or changes from baseline below/above different cut-offs (eg, <lloq assay).<="" of="" td="" the=""></lloq>
	Proportion of participants with ALT decrease and normalization.

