ICS intracellular cytokine staining

IDMC Independent Data Monitoring Committee

IEC Independent Ethics Committee
IFLEP Independent Flare Expert Panel

 $\begin{array}{ll} \text{IFN} & \text{interferon} \\ \text{IFN-}\gamma & \text{gamma interferon} \\ \text{IgM} & \text{immunoglobulin M} \end{array}$

IL interleukin

INR International Normalized Ratio
IRB Institutional Review Board
ISR injection site reaction

ITT Intent-to-treat

IU/mL International Units Per Milliliter IWRS interactive web response system

LLN lower limit of normal LLOQ lower limit of quantification

MCP-Mod Multiple Comparison Procedure-Modeling

MCT Multiple Contrast Test
MH Mantel-Haenszel
MoA mode of action

MRI magnetic resonance imaging

NA nucleos(t)ide analog

NOAEL no observed adverse effect level

PD pharmacodynamic(s)

PGIC Patient Global Impression of Change

PK pharmacokinetic(s)

PBMC peripheral blood mononuclear cell pgRNA pre-genomic ribonucleic acid

PI prediction interval

PQC Product Quality Complaint PRO patient-reported outcome

qd once daily

QTcF QT interval corrected for heart rate according to Fridericia

RBC red blood cell RNA ribonucleic acid

 $\begin{array}{lll} RNAi & ribonucleic \ acid \ interference \\ SAE & serious \ adverse \ event \\ SAP & Statistical \ Analysis \ Plan \\ SBP & systolic \ blood \ pressure \\ SD & standard \ deviation \\ SigE_{max} & sigmoid \ E_{max} \end{array}$

siRNA small interfering RNA

SUSAR suspected unexpected serious adverse reaction

 $t_{1/2 term}$ terminal half-life

t_{max} time to reach the maximum plasma concentration TAF tenofovir alafenamide

TDF tenofovir disoproxil fumarate TNF tumor necrosis factor

ULN upper limit of normal US United States WBC white blood cell

Definitions of Terms

Study intervention JNJ-73763989 or placebo, JNJ-56136379 or placebo, and NA (either ETV, TDF, or TAF)

Functional cure HBsAg seroclearance 24 weeks after end of treatment

HBsAg or HBeAg

seroclearance

HBsAg or HBeAg negativity, respectively, based on the assay used

HBsAg or HBeAg seroconversion

HBsAg or HBeAg negativity and anti-HBs or anti-HBe antibody positivity, respectively

Virologic

breakthrough

Confirmed on-treatment HBV DNA increase by >1 log₁₀ IU/mL from nadir or confirmed on-treatment HBV DNA level >200 IU/mL in participants who had HBV DNA level

<LLOQ of the HBV DNA assay

ALT/AST nadir Lowest ALT/AST value during study participation

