5.4.10. HBeAg Seroconversion

Seroconversion of HBeAg is defined as having achieved HBeAg seroclearance together with appearance of anti-HBe antibodies. The seroconversion of HBeAg will be summarized for the subset of participants with HBeAg positive at baseline.

Seroclearance of HBeAg is defined as (quantitative) HBeAg < LLOQ. Appearance of anti-HBe antibodies is defined as a baseline anti-HBe antibodies (qualitative) with a "NEGATIVE" result and a post-baseline assessment with "POSITIVE" result.

The seroconversion will only be assessed at the time points when the anti-HBe antibodies assessment is available. If the HBeAg value is missing at that specific time point, then the non-missing lab test closest to that specific timepoint will be used. If the non-missing lab test before and after the specific timepoint fall equidistant from the target timepoint, the later one will be used to impute the missing value.

The number and proportion of participants who achieve HBeAg seroconversion will be summarized by intervention arm and analysis phase.

In addition, the number and proportion of participants with appearance of anti-HBe antibodies but without seroclearance of HBeAg will also be summarized by intervention arm and analysis phase.

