5.5.4.2. Time to Appearance of Anti-HBs Antibodies

Appearance of anti-HBs antibodies is defined as a baseline anti-HBs (quantitative) <LLOQ and a post-baseline assessment \geq LLOQ.

Time to appearance of anti-HBs antibodies is defined as the time (days) from the date of first study intervention intake to the date of the first occurrence of anti-HBs antibodies appearance + 1. The participant who did not experience emergence of antibodies or who early withdrew from the study before showing emergence of anti-HBs antibodies will be censored at the last anti-HBs antibodies assessment before the date of withdrawal.

Time to appearance of anti-HBs antibodies will be analyzed in a similar manner as for the time to event endpoints described in Section 5.4.11.

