5.5.5.1. Time to Appearance of Anti-HBe Antibodies

Appearance of anti-HBe antibodies is defined as a baseline anti-HBe antibodies (qualitative) with a "NEGATIVE" result and a post-baseline assessment with "POSITIVE" result. Only participants who are negative for the anti-HBe antibodies at baseline will be included in the analysis.

Time to appearance of anti-HBe antibodies is defined as the time (days) from the date of first study intervention intake to the date of the first occurrence of anti-HBe antibodies appearance + 1. The participant who did not experience emergence of antibodies or who early withdrew from the study before showing emergence of anti-HBe antibodies will be censored at the last anti-HBe antibodies assessment before the date of withdrawal.

Time to appearance of anti-HBe antibodies will be analyzed in a similar manner as for the time to event endpoints described in the Section [5.4.11](#).

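### The SAP's seroconversion definition adds a baseline antibody-negative condition that the protocol lacks, and states no matching restriction of the denominator

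*SAP*

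**What the plan says.** The protocol lists as a secondary endpoint the "Proportion of participants with HBsAg and HBeAg seroconversion" (HBeAg in HBeAg-positive participants only). Its Appendix 1 defines seroconversion as "HBsAg or HBeAg negativity and anti-HBs or anti-HBe antibody positivity, respectively". Nothing is said about antibody at baseline.

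SAP 5.4.9 narrows this: "Seroconversion of HBsAg is defined as having achieved HBsAg seroclearance together with appearance of anti-HBs antibodies". It then adds: "Appearance of anti-HBs antibodies is defined as a baseline anti-HBs antibodies (quantitative) < LLOQ and a post-baseline assessment" at or above LLOQ, which SAP Table 3 sets at 5 mIU/mL for anti-HBs. It also says: "A sensitivity analysis will be conducted using the threshold of 10mIU/mL", with the baseline condition moved to below 10 mIU/mL. The result is a number and proportion by arm and analysis phase, with no subset named.

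SAP 5.4.10 requires anti-HBe to be negative at baseline and positive later. It does name a subset: "The seroconversion of HBeAg will be summarized for the subset of participants with HBeAg positive at baseline". That subset is defined by the antigen, not by the antibody.

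For time to antibody appearance, SAP 5.5.5.1 (anti-HBe) says: "Only participants who are negative for the anti-HBe antibodies at baseline will be included in the analysis". SAP 5.5.4.2 (anti-HBs) has no such sentence. Its censoring rule reads: "The participant who did not experience emergence of antibodies or who early withdrew from the study before showing emergence of anti-HBs antibodies will be censored". Censoring falls on the final antibody measurement.

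**The concern.** A participant who already has the antibody, clears the antigen and remains antibody-positive has seroconverted by the protocol but not by the main SAP definition. If that participant also stays in the denominator, the SAP divides a narrow numerator by a wide denominator. The result is neither the protocol's status rate nor a rate of new antibody among those who could develop it.

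Such participants are expected. The eligibility criteria in Protocol 5.1 and 5.2 do not exclude them. SAP 4.2.2 tabulates baseline anti-HBs and anti-HBe status as positive or negative, and SAP 2.4.1 makes baseline anti-HBs of 10 mIU/mL or more an efficacy subgroup. At stake are the reported level of a named secondary endpoint and the anti-HBs appearance curve.

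**Working it through.** The plan states no rate, power or prevalence for this endpoint, so there is no figure to reproduce. The check compares definitions and then bounds the size under stated assumptions.

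**1. Who counts (HBsAg cleared in every row).** The protocol gives no titre for antibody positivity; a value of 10 mIU/mL or more is taken as positive here.

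| Anti-HBs at baseline, then at clearance (mIU/mL) | Protocol | SAP main | SAP at 10 mIU/mL |
|---|---|---|---|
| <5, then ≥10 | yes | yes | yes |
| 5 to <10, then ≥10 | yes | no | yes |
| ≥10, then ≥10 | yes | no | no |

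For HBeAg the SAP has no sensitivity analysis, so anyone anti-HBe positive at baseline is excluded from the numerator throughout.

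**2. Who is in the denominator.** SAP 5.4.9 does not write it out. SAP 5 makes mITT the default efficacy set, and the mITT definition in SAP 2.3 does not mention antibody. Where the SAP wants a subset it names one, as in 5.4.10 and 5.5.5.1. The natural reading is mITT for HBsAg, and the baseline HBeAg-positive subset for HBeAg.

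**3. Size.** Let q be the share antibody-positive at baseline. Let c be the antigen clearance rate, assumed independent of baseline antibody. Let p_n and p_p be the probabilities of having antibody at clearance in baseline-negative and baseline-positive participants. None of these is in the documents.

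- Protocol rate = c[(1−q)p_n + q·p_p]
- SAP rate = c(1−q)p_n
- Ratio, SAP to protocol = (1−q)p_n / [(1−q)p_n + q·p_p]
- Shortfall, with r = p_p/p_n: q·r / [(1−q) + q·r]

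| Assumed q | r = 1 | r = 2 | r = 4 |
|---|---|---|---|
| 2% | 2.0% | 3.9% | 7.5% |
| 5% | 5.0% | 9.5% | 17.4% |
| 10% | 10.0% | 18.2% | 30.8% |

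For example, q = 10% and r = 4 gives 0.40/(0.90 + 0.40) = 30.8%. With p_n = 0.3 and p_p = 1 at q = 10%, the shortfall is 0.10/(0.27 + 0.10) = 27%. It equals q only when p_n = p_p.

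In an arm of 90 with 9 participants (10%) meeting the protocol definition:

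- q = 2%, r = 1: the SAP counts 9 × 0.98 = 8.8, or 9.8%. Limiting the denominator to the 88.2 baseline-negative participants gives 10.0%.
- q = 10%, r = 4: the SAP counts 9 × 0.90/1.30 = 6.2, or 6.9%. Over the 81 baseline-negative participants this is 7.7%.

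Whatever the response, the main SAP proportion cannot exceed 1−q.

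**4. Time to anti-HBs appearance.** The event in 5.5.4.2 requires baseline below LLOQ, but the censoring rule covers anyone without emergence. Baseline-positive participants therefore enter the risk set and are censored at their last assessment. Through the methods of SAP 5.4.11 they also enter the log-rank and stratified Cox analyses. If all have the same follow-up, the curve shows (1−q) times the incidence among those at risk: with q = 10%, a true 20% reads as 18%.

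**The case against.** The SAP version has a rationale. Appearance measures antibody that is new on study. By status alone, a participant with antibody at baseline seroconverts simply by losing the antigen, and Protocol 4.2 acknowledges a direct effect of JNJ-3989 on HBsAg. This stands as a reason to keep a new-antibody analysis. It does not explain the departure from the protocol definition, and a new-antibody rate needs a denominator of people who could develop new antibody.

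A reader might infer that baseline antibody-positive participants can never count, or that they are ignored. The documents do not support that. The 10 mIU/mL analysis lets those at 5 to <10 mIU/mL at baseline count. SAP 5.5.4.3 describes antibody change, by arm, in baseline anti-HBs-positive participants who clear HBsAg, although it does not count them as seroconverted. Nor are they labelled treatment failures, which SAP 5.4.8 defines on other grounds. HBsAg seroclearance is reported in SAP 5.4.1 with no antibody condition.

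A reader might also infer a known bias between arms. Randomisation balances baseline antibody in expectation, so no arm is systematically favoured. Chance imbalance remains possible, particularly in Arms 5 and 6 with 45 participants each. SAP 5.4.9 and 5.4.10 give descriptive summaries and name no test.

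Finally, the seroconversion denominator is inferred from the default set and the absence of a restriction. That is fair, but the inference is strong given how the neighbouring sections are written.

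**Conclusion.** The point holds in limited form. The SAP's main seroconversion definition is narrower than the protocol's, no at-risk denominator is stated, and the absolute rate is understated against the protocol definition whenever baseline antibody-positive participants clear the antigen and remain antibody-positive. The relative shortfall of 2% to 31% is illustrative only. It rests on an assumed q of 2% to 10%, an assumed r of 1 to 4, and clearance independent of baseline antibody. Taking the shortfall to be simply the baseline-positive share would need the further assumption that p_n equals p_p, which is hard to defend when one group already has the antibody.

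The gap in 5.5.4.2 is plainer, because the SAP states the needed restriction for the other antibody. The consequences are confined to a descriptively summarised secondary endpoint and an exploratory time-to-event analysis. The primary and key secondary tests do not use antibody status and are untouched.

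**What to change.** - In SAP 5.4.9 and 5.4.10, report seroconversion by the protocol definition: in the full analysis set for HBsAg, and among those HBeAg-positive at baseline for HBeAg. The SAP's existing rule for pairing antigen and antibody time points can stay. State the antibody cut-off that counts as positive.
- Report the new-antibody version as a separate, labelled analysis. Include only participants antibody-negative at baseline: anti-HBs below LLOQ (below 10 mIU/mL in the sensitivity analysis), or, within the HBeAg-positive subset, anti-HBe negative.
- Write out both denominators.
- Add to 5.5.4.2 the baseline-negative restriction already in 5.5.5.1.

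The cost is SAP wording and a denominator filter. Both antibodies are already sampled at screening and Day 1, so no new data are needed.
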